PRoFLUID statistical analysis plan

The PRoFLUID investigators

Finalized on 21-09-2025

Methods

Design

PRoFLUID is an international prospective observational cohort study in critically ill invasively ventilated patients that receive ventilation for at least 24 hours. We expect a minimum of 200 ICUs from 30 countries to participate in this study. Patients in participating centers are screened on a daily basis. Eligible patients are included during a 28-day period, from Monday at 8:00 AM to the Monday 4 weeks later at 7:59 AM (in time zones of the participating centers).

Centers are expected to include 20 consecutive patients. After this, centers can either stop study inclusion or decide to enroll more patients. Centers that decide to continue enrollment will have to enroll the next 20 consecutive patients before they are given the option to stop study enrollment, until day 28.

Data regarding fluid administration, vasopressor use, diuretics use, oxygen exchange, and kidney function will be collected daily from the start of invasive ventilation. Collection will be retrospective, for the previous day. Clinical complications will be evaluated on day 90 after start of invasive ventilation, death or hospital discharge, whichever comes first.

Patients

Patients are eligible for participation in PRoFLUID if: (I) admitted to a participating ICU; (II) receiving invasive ventilation within three days of ICU admission; and (III) having received invasive ventilation for at least 24 hours. Patients younger than 16 years, and patients that are transferred under invasive ventilation from another ICU are excluded from participation in the study.

Primary outcome

The primary outcome is the provided fluid therapy in terms of volume per indication in the first 3 days after start of invasive mechanical ventilation, particularly the volumes of resuscitation fluid.

Secondary outcome

Secondary outcomes of this analysis consider the type of fluid used during the first 3 days after start of invasive mechanical; cumulative fluid balance over the first 7 days after start of invasive mechanical ventilation; the timing of start of diuretics or ultrafiltration . Additionally, secondary outcomes will include patient related outcomes such as mortality during ICU and hospital admission; ventilator free days at day 28; and duration of ventilation in survivors and non-survivors.

Stratification

Outcomes will be analyzed across the entire cohort. Stratification will be performed over tertiles of total sequential organ failure score (SOFA) on day of intubation, specifically:

- Moderate: First tertile
- Severe: Second tertile
- Very severe: Third tertile

If SOFA components are missing at baseline, the missing values will be imputed by the mean of the patient's available component scores to calculate the total SOFA score. Patients without any data on baseline SOFA are excluded from the analysis.

Analysis plan

Descriptive statistics will be used to describe study population and fluid management parameters. Data are presented as numbers and percentages for categorical variables and as means (+/- SD) or median and interquartile range [IQR] according to distribution. Where appropriate, statistical uncertainty will be expressed by 95% confidence intervals.

We will describe the volume per indication for intravenous fluid therapy over the following indication categories:

- Resuscitation fluid
 - Prescribed in response to hemodynamic impairment or shock
 - Usually, isotonic crystalloids or colloids
 - At a rate of at least 166ml/h (1L/6 hours)
 - Usually much faster or as a bolus
- Maintenance or replacement fluid:

- Maintenance Fluids
 - Cover daily water and electrolyte needs
 - Up to 100 ml/h infusion rate.
- Replacement fluids
 - To address fluid losses
 - For example given for burns, dehydration, losses through drains, keto-acidosis
 - Can have faster (e.g. > 100ml/h) infusion rates
 - Are not given as bolus
- Unknown indication
 - Prescribed intravenous fluid therapy for which it is impossible to distinguish between resuscitation, maintenance or replacement

The volumes of intravenous fluid therapy per indication will also be examined in the context of all other fluids that are provided:

- Fluid as a carrier for intravenous medication
- Fluid to ensure catheter patency
- Cellular blood product transfusion
- Oral feeding
- Oral fluids
- Parenteral feeding

These volumes will be described as absolute mean volumes in mL with 95% confidence interval, as mean volumes per kilogram of body weight with 95% confidence interval, and relative to each other (as percentage of total).

Fluid volumes will be plotted using cumulative distribution plots that display fluid volumes over the first 3 days after intubation.

To adjust for case-mix differences across SOFA tertiles and investigate factors that influence fluid management, multivariate regression analysis will be performed, adjusting the administered fluid volumes for the following baseline variables: duration of first study day; sex; age; weight; and admission diagnosis. The differences in fluid administration between SOFA tertiles be evaluated.

Secondary endpoints may be described and differences in the distributions between SOFA tertiles regions may be tested using regression analysis or Kruskal-Wallis test. Associations between fluid balance and clinical outcomes will be assessed using Cox proportional hazards modelling with fluid balance as a time-dependent covariate. The model will be adjusted for duration of day 0, age, sex, weight, baseline SOFA, and admission diagnosis. Other covariates may also be considered for the model if deemed appropriate.

Sensitivity testing will be performed to assess the robustness of findings. All statistical analyses will be performed using R. We consider $p < 0.05$ to be statistically significant.

Table 1 – Minimal list of proposed tables and figures

	Description
Main paper	
Table 1	Baseline Characteristics
Table 2	Clinical outcomes
	Cumulative distribution of volumes per indication for fluid administration over the first 3 days after intubation:
Figure 1	A four panels figure showing: A) Cumulative distribution of volume of resuscitation fluid per stratifying variable; B) Cumulative distribution of volume of maintenance or replacement fluid per stratifying variable C) Cumulative distribution of volume of IV medication per stratifying variable; and D) Cumulative distribution of volume of cellular blood product transfusion per stratifying variable
	Fluid input, output and balance over first 7 days after intubation
Figure 2	A three panels figure of line plots with 95% CI showing: A) total volume of fluid volume input per admission day by stratification variable; B) total volume of fluid volume output per admission day by stratification variable; C) Daily fluid balance by stratification variable.
	Types of fluid prescribed
Figure 3	A two panels figure of stacked bar plots showing proportional fluid composition. Panel A reports the proportional distribution of major fluid categories Panel B details the composition of the 'other' fluid category by SOFA class, Proportions are expressed relative to the total volume of fluid administered within each SOFA class.
Online Supplement	
eTable 1	Steering committee
eTable 2	National coordinators
eTable 3	Participating centers
eTable 1	Proportion of missing data per variable
eTable 2	Mean volumes per indication for fluid administration per study day and stratification variable.
eTable 3	Mean volumes per type of fluid per study day and stratification variable.
eTable 4	Factors associated with fluid management
eTable 5	Results of multivariate regression for the association of fluid balance and mortality
eFigure 1	Participant flow diagram
eFigure 2	Cumulative distribution of volumes per indication for fluid administration for other indications
eFigure 3	Proportional volume of fluid type per day and stratification variable.
eFigure 4	Daily serum lactate, sodium and chloride.
eFigure 5	Daily SOFA over the three days after intubation Line plot reporting A) total SOFA, B) cardiovascular SOFA, C) respiratory SOFA, and D) renal SOFA according to randomization group. Mean and 95% confidence intervals will be reported.

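### The fluid-volume regression does not adjust for time from ICU admission to ventilation, so its comparison across SOFA tertiles may be partly confounded by where in the ICU course counting began

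*SAP*

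**What the plan says.** Under Patients, criterion II requires "receiving invasive ventilation within three days of ICU admission". This sets an upper limit on the delay and no lower limit.

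Under Design, the fluid data "will be collected daily from the start of invasive ventilation". The SAP describes no collection of fluid given earlier.

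Under Primary outcome, the target is "volume per indication in the first 3 days after start of invasive mechanical ventilation, particularly the volumes of resuscitation fluid". Time zero is thus the start of ventilation, not ICU admission.

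Under Stratification, the cohort is split by "tertiles of total sequential organ failure score (SOFA) on day of intubation".

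Under Analysis plan, a regression of fluid volume is planned, with two aims: "To adjust for case-mix differences across SOFA tertiles and investigate factors that influence fluid management". Its covariates are listed as "duration of first study day; sex; age; weight; and admission diagnosis". The interval from ICU admission to ventilation is not among them. The sentence "Other covariates may also be considered for the model if deemed appropriate" comes after the description of the Cox model, not after this regression. The plan adds that "Sensitivity testing will be performed to assess the robustness of findings", but does not say what will be tested.

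**The concern.** Resuscitation fluid is the volume of most interest in this study, and the SAP defines it as fluid prescribed for haemodynamic compromise. A patient ventilated soon after ICU admission is likely to have ICU resuscitation counted. A patient ventilated on the second or third ICU day may have received much of it before counting starts. Two patients with the same SOFA score on the day of intubation can therefore show different volumes in the window simply because they entered it at different stages of their ICU course.

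The adjusted tertile comparison is meant to remove differences in case mix. If the interval differs between tertiles after the listed covariates are taken into account, and if it also predicts later volume, part of the adjusted difference reflects when counting began. The second aim of the regression, finding factors that influence fluid management (reported in eTable 4), is also served less well if this candidate is not in the model.

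**Working it through.** The SAP gives no sample size, effect size or delay distribution tied to this point, so it contains no figure to reproduce. The check is first textual, then an illustration of size under stated assumptions.

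**Textual check**

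| Item | What the SAP fixes | Place |
|---|---|---|
| Delay before time zero | Up to three days after ICU admission, no lower limit | Patients, criterion II |
| Start of fluid counting | Start of ventilation | Design; Primary outcome |
| Timing of the SOFA score | Day of intubation | Stratification |
| Covariates of the fluid regression | Five, none of them the delay or earlier fluid | Analysis plan |
| Open clause for more covariates | Attached to the Cox model | Analysis plan |

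The listed duration of the first study day does not fill the gap. It measures how long the first observation day lasted, not how much ICU time came before it.

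Delay accrues before intubation. It is therefore not a step on a path from the intubation-day SOFA score to later fluid, and adjusting for it does not remove part of such an effect.

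**Illustration of size (all inputs assumed)**

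The omitted-variable formula for the contrast of top with bottom tertile is

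bias = (mL per day of delay) × (top minus bottom tertile difference in mean delay, in days).

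In an adjusted model, the second factor is the difference that remains after the listed covariates are accounted for.

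| Slope (mL per day) | Difference -0.5 d | -0.25 d | 0 | +0.25 d | +0.5 d |
|---|---|---|---|---|---|
| 0 | 0 | 0 | 0 | 0 | 0 |
| -100 | +50 | +25 | 0 | -25 | -50 |
| -250 | +125 | +62.5 | 0 | -62.5 | -125 |
| -500 | +250 | +125 | 0 | -125 | -250 |

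The range is -250 to +250 mL, and the bias is zero whenever either factor is zero.

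**Check by simulation**

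One least-squares simulation per scenario was run with n = 4,000, 60% of patients with no delay and 40% with a delay uniform over 0 to 3 days, a slope of -500 mL per day, a true step of 400 mL per tertile (so a true top-minus-bottom difference of 2 × 400 = 800 mL), a residual SD of 1,500 mL and no other covariates.

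| Difference in mean delay | Contrast without delay in the model | Contrast with delay | Gap | Formula |
|---|---|---|---|---|
| -0.55 d | 1,064 mL | 782 mL | +282 mL | -500 × -0.55 = +275 |
| +0.59 d | 493 mL | 803 mL | -310 mL | -500 × 0.59 = -295 |
| +0.01 d (delay unrelated to SOFA) | 687 mL | 690 mL | -3 mL | -500 × 0.01 = -5 |

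The simulation agrees with the formula. Without delay in the model the contrast can be too high, too low or right, depending on facts that the SAP does not give. (In the third row both estimates fall below 800 mL by sampling error alone.)

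**Scale of the study**

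The SAP expects at least 200 ICUs, with 20 patients each: 200 × 20 = 4,000 patients. One or two further covariates cost next to nothing in precision at that size.

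**The case against.** The strongest reply is that nothing here is shown to be biased. A reader might infer that earlier ICU fluid does confound the tertile comparison, or that the contrast is off by some definite amount in a known direction. The SAP supports neither. Confounding needs delay to be related to SOFA tertile and to later volume, given the covariates already in the model, and the document shows neither link. That part of the objection stands in full.

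A second reply is that the primary outcome is descriptive and is defined from the start of ventilation, so earlier fluid lies outside it by design. This also stands. The crude volumes, their breakdown by tertile and the cumulative distribution plots are not wrong on this ground. Only the adjusted comparison and the search for influencing factors are touched.

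A third reply is that SOFA is used to stratify by severity, without a causal claim, so that adding delay changes the question rather than correcting an error. This has some force, because the SAP does not fix the question precisely. But the regression's own stated aims are case-mix adjustment and the identification of factors, and a pre-intubation interval fits both.

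A fourth reply is that delay is a weak proxy. Fluid given in an emergency department, theatre or ward is uncounted even for a patient ventilated on ICU arrival, and patients ventilated before arrival started their clock earlier still. This stands, and it shapes the fix.

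A fifth reply is that criterion II could be checked as a yes or no, so the interval may not be recorded. The SAP does not settle this. The start of ventilation must be known because it is time zero, so the only further item needed is the ICU admission time. The protocol, which is not shown, may already provide for it.

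Finally, the table list is labelled minimal and the contents of Table 1 are not itemised, so the interval may already be planned for display there. That would meet half of the request, but would not put the interval into the regression.

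**Conclusion.** The point holds as a modest gap. Counting begins at ventilation, ventilation may begin up to three days into the ICU stay, and the covariates fixed for the fluid-volume regression do not include that interval. The adjusted tertile comparison may therefore be partly confounded, and a plausible driver of volume is left out of the model.

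Neither the size nor the direction can be derived from the SAP. The range of -250 to +250 mL rests entirely on assumed slopes and delay differences, and zero lies within it. The conclusion does not extend to the descriptive primary volumes. Nor does it require a change to the Cox model: no argument on this ground has been made for that model, and its covariate list is in any case left open.

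This is a worthwhile improvement to a supporting analysis, not a threat to the study's main description.

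**What to change.** 1. Derive the time from ICU admission to the start of invasive ventilation from the times needed to check criterion II.
2. Report it by SOFA tertile in the paper's baseline table (Table 1). This shows directly whether the tertiles differ in delay.
3. Add it to the covariates of the fluid-volume regression, together with an indicator that separates patients ventilated before ICU arrival from those ventilated on or after arrival, so that the two groups are not pooled at zero delay.
4. State as a limitation that the interval is only a proxy for earlier fluid and does not capture fluid given before ICU admission.

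The cost is one derived variable and one indicator, negligible against about 4,000 expected patients, provided that the ICU admission time is recorded. The small downside is that readers may take the adjustment to have dealt with earlier fluid, which is why the limitation should be written into the SAP.

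### If the optional SOFA-tertile test is applied to ventilation duration within survivors or non-survivors, it mixes liberation with death and should give way to a competing-risk comparison

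*SAP*

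**What the plan says.** Under Secondary outcome, the SAP names "duration of ventilation in survivors and non-survivors" among the patient-related outcomes, next to "mortality during ICU and hospital admission; ventilator free days at day 28". Under Stratification, outcomes are analysed in the whole cohort, and "Stratification will be performed over tertiles of total sequential organ failure score (SOFA) on day of intubation"; the groups are labelled moderate, severe and very severe.

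Under Analysis plan, the rule for these outcomes is permissive: "Secondary endpoints may be described and differences in the distributions between SOFA tertiles regions may be tested using regression analysis or Kruskal-Wallis test". I read the word regions there as stray. The threshold is general: "We consider $p < 0.05$ to be statistically significant".

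No competing-risk or cumulative-incidence method is named for time to liberation. The Cox model in the same section relates fluid balance to clinical outcomes; it does not compare tertiles on liberation.

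**The concern.** Survival status is settled after ventilation starts, and death on the ventilator competes with liberation. Where the death hazard is higher, patients who would have had long courses are more likely to die before liberation and drop out of the survivor group. The survivors who remain have shorter courses on average. A test between tertiles within survivors therefore compares differently selected patients.

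The non-survivor group has a related problem. Its durations combine time to death on the ventilator with time to liberation in patients who die later.

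At stake is the reading of one secondary outcome. A significant tertile difference could be taken as faster liberation in the sickest patients when liberation rates are equal. A null result could hide slower liberation.

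**Working it through.** The SAP gives no liberation rate, death rate or sample size, so there is no planned figure to reproduce. What follows is an illustration.

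**Inputs from the SAP.** Eligibility requires "having received invasive ventilation for at least 24 hours", modelled as a 1-day offset. On size, "We expect a minimum of 200 ICUs from 30 countries to participate in this study", with 20 patients expected per centre: 200 × 20 = 4,000. A cohort of 1,500 is used as a smaller alternative.

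**Assumed.** After 24 hours, liberation hazard L and death hazard M are constant within each tertile.

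**Formula.** The time to whichever event comes first is exponential with rate L + M, whichever event it is. Among patients liberated alive:

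median duration = 1 + ln 2 / (L + M)

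This falls as M rises, even when L is fixed. Example with L = 0.10 and M = 0.02, 0.035, 0.05:

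- 1 + 0.693/0.120 = 6.8 days
- 1 + 0.693/0.135 = 6.1 days
- 1 + 0.693/0.150 = 5.6 days

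**Scenarios** (values run from first to third tertile; rejection is Kruskal-Wallis p < 0.05 in survivors, by simulation):

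| | L per day | M per day | Survivor median, days | Rejection, 1,500 | Rejection, 4,000 |
|---|---|---|---|---|---|
| A | 0.10 in all | 0.01/0.02/0.03 | 7.3/6.8/6.3 | about 44% | about 86% |
| B | 0.10 in all | 0.02/0.035/0.05 | 6.8/6.1/5.6 | about 65% | about 97% |
| C | 0.10 in all | 0.02/0.04/0.08 | 6.8/6.0/4.9 | about 99% | 100% |
| D | 0.10/0.085/0.07 | 0.02/0.035/0.05 | 6.8/6.8/6.8 | about 5% | about 5% |
| E | 0.10/0.075/0.05 | 0.02/0.035/0.05 | 6.8/7.3/7.9 | not needed | not needed |

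Repeat simulations of A and B vary by up to about 3 percentage points.

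**Control.** With equal mortality in all tertiles and L = 0.10, rejection is about 5%. The differences in A to C therefore come from conditioning on survival.

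**Scenario D.** L + M is 0.12 in every tertile, so the survivor durations have the same distribution. The liberation hazard in the third tertile is 1 − 0.07/0.10 = 30% lower than in the first, and the test cannot see it.

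**Scenario E.** The direction is right but the contrast is shrunk. Without competing death, 1 + ln 2/L would give 7.9, 10.2 and 14.9 days.

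**Deaths after liberation.** Adding these at 5/10/15% to A gives rejection of 42% and 84%. Adding 5/10/20% to C gives 97% and 100%. The effect does not depend on ignoring them.

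**What the alternative shows.** The cumulative incidence of liberation alive to day 28 is L/(L + M) × (1 − exp(−27(L + M))), with 28 − 1 = 27 days at risk. In B this is 0.80, 0.72 and 0.66; in D it is 0.80, 0.68 and 0.56. The curve falls with severity in both, because death lowers it too, so the cause-specific hazard ratios are needed beside it. For the third tertile against the first:

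- B: liberation 0.10/0.10 = 1.00; death 0.05/0.02 = 2.5.
- D: liberation 0.07/0.10 = 0.70; death 0.05/0.02 = 2.5.

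These ratios separate the two cases; the survivor-only test does not.

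**The case against.** The strongest reply is that the SAP does not commit to this test. It says secondary endpoints may be described and tertile differences may be tested, as an option across all of them. A reader might infer a firm plan to compare survivors' ventilation between tertiles; the text does not support that. It does permit the test, sets a threshold and exempts no outcome.

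Second, the study is descriptive, its primary outcome is fluid volume, and the SAP states no hypothesis about liberation. Duration among survivors is a legitimate description and misleads only if read as a liberation rate. This stands, and it is why the durations should stay.

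Third, mortality and ventilator-free days are reported alongside. Mean ventilator-free days fall with severity in the same model (16.7/15.8/15.0 in A; 15.8/14.3/11.9 in C). A reader who sees these is unlikely to conclude that the sickest do better overall. This limits the harm, but neither outcome isolates liberation.

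Fourth, equal liberation rates are doubtful in groups defined by organ failure. A reader might infer that the sickest tertile will appear to leave the ventilator sooner. That is not established: direction and size depend on hazards the SAP does not give, and scenario E goes the right way. Offsetting effects do not make the test safe, however, as D shows.

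**Conclusion.** The point holds conditionally and is minor. If the optional tertile test is applied to ventilation duration within survivors or non-survivors, its result reflects death as well as liberation. It can signal a difference when liberation is equal (A to C), hide a real one (D) or understate it (E).

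The percentages rest on assumed constant hazards and on assumed cohorts of 1,500 or 4,000. They show what can happen and do not predict this study's results.

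A reader might also infer that duration in non-survivors is simply time to death on the ventilator. The documents do not support that: hospital mortality is an outcome, so non-survivors can include patients liberated before they died. The primary outcome, the fluid analyses and the planned Cox model are not affected.

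**What to change.** In the Analysis plan section, state that duration of ventilation in survivors and in non-survivors is reported by tertile as median and IQR, with no between-tertile test.

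For the comparison of tertiles, specify the cumulative incidence of liberation alive to day 28 with death as a competing event (Aalen-Johansen curves). Add cause-specific hazard ratios for liberation and for death, and present the two together. Define liberation as for ventilator-free days, and start the curve at 24 hours because every included patient is still ventilated then.

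The descriptive part is already within what the SAP allows. The cost is a few lines of SAP wording, plus one more analysis and curve to present. The analysis uses data already needed for the planned duration, mortality and ventilator-free-day outcomes.

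### The adjusted fluid-volume regression uses SOFA only as sample-based tertiles, so the shape of the severity–volume relation stays hidden although a numeric score is available

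*SAP*

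**What the plan says.** The Stratification section of the SAP sets the grouping: "Stratification will be performed over tertiles of total sequential organ failure score (SOFA", taken on the day of intubation, in three classes, running from "Moderate: First tertile" to "Very severe: Third tertile". No score ranges are attached to the labels.

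The same section shows that a numeric score exists before it is cut. If components are missing, "the missing values will be imputed by the mean of the patient's available component scores to calculate the total SOFA score"; patients with no baseline SOFA data at all are excluded.

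Under Analysis plan, the regression of administered fluid volumes adjusts for "duration of first study day; sex; age; weight; and admission diagnosis". On severity it says: "The differences in fluid administration between SOFA tertiles be evaluated". The covariate list has no continuous SOFA term. Results on factors associated with fluid management are listed as eTable 4.

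The Cox model for fluid balance and clinical outcome is separate: "The model will be adjusted for duration of day 0, age, sex, weight, baseline SOFA, and admission diagnosis". Whether SOFA enters there as a score or as tertiles is not stated. Sensitivity testing is announced without content.

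**The concern.** Tertiles are a reasonable way to lay out tables and figures. Here they are also the only form in which SOFA is named for the inferential model of fluid volume. That model treats all patients within a third as equally ill and places a jump between two neighbouring scores, at a point set by whoever was enrolled.

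Three consequences follow.

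- **Shape.** The regression is meant to investigate what influences fluid management. Three group means cannot show whether volume rises steadily with severity, levels off, or changes at a threshold.
- **Meaning of the labels.** The class names are ranks within this sample. Unless the observed score ranges are reported, a reader cannot tell which patients a moderate or very severe class contains.
- **Precision.** If the relation is close to linear, grouping discards part of the information in a score that is already computed.

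**Working it through.** The SAP gives no sample size, power, SOFA distribution or effect shape, so there is no figure of its own to reproduce. Everything below rests on stated assumptions.

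**1. Information kept by tertiles: normal score, linear effect.** With an outcome linear in the score, the relative efficiency of a three-group analysis is the between-group share of the score's variance. For a standard normal cut at its tertiles:

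- Upper cut z = 0.4307, density φ(z) = 0.3636.
- Mean of the upper third = 3 × 0.3636 = 1.0908; the lower third has the opposite sign and the middle third has mean 0.
- Between-group share = (2/3) × 1.0908² = 0.793.
- Loss = 1 − 0.793 = 0.207, or about 21%. Standard errors grow by 1/√0.793 = 1.12, or about 12%.

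**2. Dependence on the assumed distribution (linear effect throughout).**

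| Assumed score | Information lost |
|---|---|
| Normal | 20.7% |
| Integer 0–24, mean 6–11, SD 3–4.5 | 17–23% |
| Uniform, integer 0–24 | 11% |
| Right-skewed gamma, shape 8 to 1 | 23–35% |

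**3. Dependence on the effect shape.** If volume truly jumps at the upper tertile and is flat elsewhere, the tertile model captures all of it, and a straight line captures about 59%. The losses in step 2 then do not apply.

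**4. Ties.** For an integer score with assumed mean 8 and SD 3, the group sizes depend on where the tied scores go:

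| Cuts | Group shares | Variance kept |
|---|---|---|
| 0–7, 8–9, 10–24 | 43%, 26%, 31% | 77.9% |
| 0–6, 7–8, 9–24 | 31%, 26%, 43% | 77.7% |
| 0–6, 7–9, 10–24 | 30.6%, 38.5%, 30.8% | 81.6% |

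The SAP does not say how tied scores are allocated. Unequal groups do not invalidate the regression, but membership at the cut scores is left open. Totals with mean-imputed components need not be integers, so this is an illustration only.

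**5. What the change would recover.** The Design section expects at least 200 ICUs and 20 patients per centre. The product, 200 × 20 = 4,000, is used for illustration and is not a planned sample size. Take a linear relation, two-sided alpha 0.05 (the SAP gives 0.05 without sidedness) and no clustering by centre. The noncentrality for the full score is 4,000 × r²/(1 − r²), which is 10.03 at a correlation r = 0.05. For tertiles, r² is first multiplied by 0.793, which gives 7.95. Power of the overall test of association at r = 0.05:

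| SOFA term | df | Power |
|---|---|---|
| Linear | 1 | 0.89 |
| Spline, 3 knots | 2 | 0.82 |
| Spline, 4 knots | 3 | 0.76 |
| Spline, 5 knots | 4 | 0.72 |
| Tertiles | 2 | 0.71 |

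At r = 0.08 all of these exceed 0.98. The power gain is therefore confined to weak associations, and a spline with many knots gives most of it back.

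**The case against.** The strongest reply is that nothing here is an error. Tertiles are openly pre-specified, the primary outcome is descriptive, and outcomes are analysed over the whole cohort before any stratification. Grouping SOFA costs those cohort-wide estimates nothing. That stands, and it limits the point to one adjusted model. A reader might infer that severity against fluid volume is the study's main comparison, but the Primary outcome section does not support this.

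It can also be said that a loss of a fifth is an assumption and not a property of the plan. That stands as well: the SAP gives neither the distribution nor the effect shape, and step 3 shows a case with no loss. It is tempting to express the loss as patients discarded, about 830 of 4,000 (4,000 × 0.207). That would mislead: 4,000 is not a stated sample size, and the figure compares tertiles with a linear term, while a spline spends further degrees of freedom.

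A reader might further conclude that the results cannot be carried to other cohorts. The documents do not support that. Observed cut-points can be reported and reused, and the SAP's Table 1 is a minimal list that leaves room to add them.

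The unspecified sensitivity testing does not answer the point, because no continuous-SOFA analysis is named in it. Nor does the Cox model's SOFA covariate, which belongs to a different analysis.

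**Conclusion.** The point holds as an inexpensive improvement to the adjusted fluid-volume regression, not as a fault in the study's main results. The SAP names SOFA there only as sample-based tertiles without numeric cut-points, although the numeric total is in hand. This imposes flat segments and sample-dependent steps, and it conceals the form of the relation.

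The precision cost is conditional. It is about 21% of the information for a normal score with a linear effect, roughly 11–35% over the other distributions tried, and zero for a step located at a tertile. With several thousand patients it would matter only for weak associations. The firmer grounds for change are the hidden shape and the labels that have no stated score range.

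**What to change.** - Keep tertiles for the tables and figures. Label each class with its observed SOFA range and group size, and state in the SAP how tied scores at a cut are allocated.
- In the adjusted regression (eTable 4), add a model with total SOFA as a continuous term: a restricted cubic spline with few knots, for example 3, fixed in advance, with a linear term also reported.
- Show predicted resuscitation volume across SOFA with 95% CI, alongside the tertile contrasts.

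The cost is one extra model and one supplementary plot, with no new data. The drawback is that a spline is read as a curve and not as a single coefficient; reporting the linear term as well partly offsets this.
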